8.2 Informed consent

The investigator ensures that each study subject is provided with full oral and written information about the nature, purpose, expected advantages and possible risks of the study, has been given an opportunity to ask questions about the study and the involvement and has received answers to all such questions. Further, the investigator ensures that no patient will be enrolled into the study without prior obtaining of written informed consent which is to be dated and signed by the patient and by the investigator or sub-investigator who provided the information. The final versions of patient information and consent will be presented to the Ethics Committee. Both the patient information and the patient consent form are prepared in duplicate. One of each form for the Investigator, a duplicate will be handed to the patient.

8.3 Copeptin testing

Copeptin will be requested from the laboratory to be tested in the surplus routine blood samples after the informed consent has been signed.

8.4 Enrolment and randomization

Patients will be assigned to their study group by randomization via sealed envelopes as soon as the written informed consent has been signed.

The Copeptin test result will not automatically be communicated to the Emergency Department but will need to be requested via telephone after the randomization. It will only be released for patients in the experimental group. To assure this, the randomization letter for patients in the experimental group will contain a code which will be noted down in the central laboratory before releasing the Copeptin value.

The code can be compared with the code in the patient's randomization letter to proof adherence to this process.

In patients who are randomized to the control group, the Copeptin result will only be documented at the laboratory and will not be available to the investigators during the recruitment period.

8.5 Registration

Patients, who meet all inclusion criteria, who have given their written informed consent and have been randomized will be reported to the trial centre via Fax.:

- BIC-Trials
- [name]

The following data are to be included in this registration FAX (attachment 6)

- Study site, Investigator
- Pseudonym of patient
- Gender
- Randomization group

The trial centre will regularly (1x/week) update the members of the steering committee on the numbers and basic characteristics (s. above) of patients enrolled.

8.6 Clinical processes

Procedure	Screening	Enrolment	Randomization	Discharge	30d	90d
Screening Log	x					
Medical history	x					
Physical exam.	x					
Routine -ECG	x					
Blood routine*	x					
Copeptin		x**				
Informed consent		x				
Copeptin result request			(x) ***			
Questionnaire contentedness				x		
MACE and bleeding event assessment				x	x	x

- Including Troponin and CK

**request from routine blood sample from screening period

*** only for patients in experimental group

All in-hospital examinations are standard practice of care in patients with suspected ACS. The deviations concern the process of patient management – early discharge of Copeptin negative patients and further evaluation of high-risk ACS of Copeptin positive patients - rather than in-hospital examinations. All CPU patients are under constant monitoring and risk assessment.

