Objectives	To quantify the benefit of integrating the new biomarker Copeptin into the process of managing patients with suspected non ST-elevation acute coronary syndrome (N-STEACS) with a negative baseline Troponin test result in the Emergency Department. Hypothesis : Patients with suspected ACS with a negative baseline Troponin who test negative for Copeptin at admission are at low risk of ACS and can safely be discharged into ambulant care. Secondary hypotheses: Patients with suspected ACS with a negative baseline Troponin who test positive for Copeptin at admission are at risk for ACS and should be evaluated as by standard of care. The Integration of Copeptin into the CPU process will shorten the patient's length of Emergency Department/ CPU and hospital stay and will improve patient satisfaction.
Study Design	Multicentre, open, randomized, controlled clinical trial (RCT) Interventional diagnostic biomarker trial 1:1 Randomization in two study arms with differing process management: a) interventional/experimental arm (Integration of Copeptin) b) control/ standard arm (Copeptin not available to treating staff)
Number of Sites	3 sites in Germany, 1 site in Switzerland and 1 site in Austria
Experimental Diagnostic Process	Experimental Arm: Patients with the above described characteristics who test negative for Copeptin at admission will be considered low-risk and will be discharged into ambulant care without further interventions. Patients with the above described characteristics who test positive for Copeptin at admission will be evaluated as by standard of care according to current guidelines..
Standard Diagnostic	Control Arm:

Process	Copeptin result will not be revealed to the treating physicians. Patients will be evaluated as by standard of care according to current guidelines.
Gold Standard	DGK / ESC / AHA Guidelines for the management of patients with suspected Non-ST-elevation ACS (NSTEMACS)
Time Schedule	Date of study / recruitment start: February 2011 Date of termination of recruitment: February 2012 Date of study termination: Autumn 2012
Total Number of Patients	n=446 per treatment group (total number of patients 892)
Study Population	Men and women of full age with suspected Non-ST-elevation acute coronary syndrome (NSTEMACS) and negative baseline Troponin.

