5 Study objectives

This is a multicentre biomarker randomized controlled trial to quantify the benefit of integrating the new biomarker Copeptin into the process of managing patients with suspected non ST-elevation acute coronary syndrome (N-STEACS) with a negative baseline Troponin I test result in the Emergency Department and Chest Pain Unit.

Hypothesis:

Patients with suspected ACS with a negative baseline Troponin who test negative for Copeptin at admission are at low risk of ACS and can safely be discharged into ambulant

care. These patients will not experience a higher rate of MACE within 30 days after their admission than patients who are managed by standard practise of care.

Secondary hypotheses:

Patients with suspected ACS with a negative baseline Troponin T who test positive for Copeptin at admission are at risk for ACS and should be evaluated as by standard of care. The Integration of Copeptin into the CPU process will shorten the patient's length of Emergency Department/ CPU and hospital stay and will improve patient satisfaction

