7.1 General Patient Flow

Consecutive N-STEACS patients of the Chest Pain Unit with a negative Troponin T at admission will be invited to participate. Troponin T is tested as part of the standard management of patients with suspected acute coronary syndrome. Patients who give their written informed consent will be randomized into one of two study arms (experimental and standard management).

Experimental Arm: Further management dependent on Copeptin result

1. Patients of the above described characteristics who test **negative for Copeptin** at admission will be considered low-risk. In these patients we abstain from further ACS evaluation and instead discharge them into ambulant care. Before discharge patients will have a final visit to secure their well-being. The visit includes a physical examination, an ECG and an assessment for MACE and bleeding events.

Patients who show any signs and symptoms of an acute illness requiring in-hospital treatment will not be discharged (see withdrawal criteria 5.3). This decision is at the discretion of the attending physician.

To secure the patients safety they will be discharged into each co-operating network of resident cardiologists . Patients are to see a cardiologist within a maximum of 3 days after discharge (if discharge falls on a Friday), preferably on the next day after discharge. Further appointments will be at the discretion of the resident cardiologist (see 7.2).

2. Patients with the above described characteristics who test **positive for Copeptin** at admission will be managed as by standard practice i.e. patients will be evaluated as by standard of care abiding current guidelines for the management of patients with suspected ACS

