8.9 Additional 3 hour blood test

Patients can, on an optional basis, agree to an additional, study-related blood draw at 3 hours after their initial admission. This blood sample will be used to further evaluate the kinetics of Copeptin. Additionally, Troponin will be measured to compare the two markers in these samples.

Patients who agree to the blood draw have to give their separate written consent in a special box of the informed consent form (s. attachment).

9 Risk-benefit-assessment

Copeptin negative patients might experience major adverse cardiac events after discharge, which could have been prevented in case of hospital admission, due to unrecognized acute coronary syndrome.

Precaution:

Patients for this trial are very carefully selected. Patients with concomitant diseases or conditions which require a hospitalisation as well as patients with instable angina despite maximal therapy are excluded from participation. Thus, only stable, symptom-free patients will be discharged. We cannot exclude that of these patients, some will be at risk for ACS-related complications. As a precaution, patients will only be discharged after an appointment with one of our co-operating resident cardiologists has been made via the praxis-connect system as explained in section 7.1. Thus, the onward specialist care of these patients is guaranteed. The co-operating cardiologists will be well informed and trained in all trial-matters. All patients will be re-admitted to the Emergency Department upon any suspicion of risk for complications.

Copeptin positive patients might be regarded as high-risk patients and receive more intensive treatment.

Precaution:

Management of all patients will be closely monitored by the principal investigator of each site to assure suitable care and therapy.

Potential advantages for patients in the experimental arm:

Copeptin negative patients bypass further ACS evaluation and are prevented from hospitalization. Patients might be spared an unnecessary hospital admission and antithrombotic and anticoagulant treatment with their related hazards and side-effects. Patients will profit from the personal care by the resident co-operating cardiologist.

All patients will profit from the close and intense monitoring and follow-up by an experienced clinical research team.

Potential advantages for the general public:

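### Section 8.6 lists the care of Copeptin-positive patients as a deviation, while the synopsis, section 5 and section 7.1 make it standard care, which leaves the whole-arm secondary results open to misreading

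*Protocol*

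**What the plan says.** Three places in the Protocol agree. The synopsis, under the experimental process, says: "Patients with the above described characteristics who test positive for Copeptin at admission will be evaluated as by standard of care according to current guidelines". The secondary hypothesis in section 5 describes patients "who test positive for Copeptin at admission are at risk for ACS and should be evaluated as by standard of care". Section 7.1 says they "will be managed as by standard practice i.e. patients will be evaluated as by standard of care abiding current guidelines". Section 7.5 sets the same standard for the control arm, with the Copeptin result withheld.

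Section 8.6 reads differently. It opens with "All in-hospital examinations are standard practice of care in patients with suspected ACS" and continues "The deviations concern the process of patient management". It then names two deviations in one phrase: "early discharge of Copeptin negative patients and further evaluation of high-risk ACS of Copeptin positive patients". The sentence ends by setting these deviations apart from in-hospital examinations.

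Section 9 lists among the risks that "Copeptin positive patients might be regarded as high-risk patients and receive more intensive treatment". The precaution given there is oversight of patient management by each site's lead investigator.

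Under section 8.4 the Copeptin value is released only for the experimental group. Control-arm values are kept at the laboratory and withheld from investigators while recruitment runs. Section 5.2.5 predefines three subgroup factors: sex, GRACE score and age. Copeptin status is not among them.

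**The concern.** Care cannot be both standard and a deviation from standard. On a literal reading of 8.6, the experimental strategy changes management for positives as well as negatives, and positives carry a high-risk label. The synopsis, section 5 and 7.1 do not use that label. On those passages, the only change is early discharge of negatives.

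This matters because the endpoints are compared between whole arms, while the main hypothesis in section 5 concerns Copeptin-negative patients. Early discharge would be expected to lower angiography, PCI, bleeding and length of stay. More intensive care of positives, if it happened, could raise them. A small or null whole-arm difference could then mean that little changed, or that two changes offset each other. The primary endpoint is exposed too, because MACE in sections 5.1 and 11.1 includes acute unplanned PCI and CABG.

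**Working it through.** **Text comparison.** The Protocol gives no figure for this point, so there is none to reproduce. The passages compare as follows.

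| Place | Care of Copeptin-positive patients, experimental arm |
|---|---|
| Synopsis | Standard, by guidelines |
| Section 5, secondary hypothesis | At risk for ACS; standard |
| Section 7.1 | Standard, by guidelines |
| Section 8.6 | Named as a deviation, with a high-risk label; no procedure specified; examinations standard |
| Section 9 | More intensive treatment possible, listed as a risk |

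Section 8.6 therefore conflicts with three statements on whether care of positives departs from standard. It does not say what the departure would be.

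**Route into the results.** By 8.4 only experimental-arm staff can react to a positive result, so any reaction occurs in one arm and passes into the whole-arm contrast.

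**How large it could be.** The only input from the Protocol is 446 patients per arm (synopsis). The share positive at 10 pmol/L, the angiography rate and the change in positives are not given. All three are assumed below, to show a range and not to estimate an effect.

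*Shift in the arm rate.* Assume 20 to 40% positive and a rise of 10 to 20 points among them.
- Patients affected: 446 × 0.20 = 89, to 446 × 0.40 = 178.
- Whole-arm shift = share × rise: 0.20 × 0.10 = 0.02, to 0.40 × 0.20 = 0.08.
- Standard error of the arm difference at an assumed 30% base rate: √(2 × 0.3 × 0.7 / 446) = 0.031.
- The shift is 0.65 to 2.6 standard errors.

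*Offsetting changes.* Assume control angiography of 30% in negatives and 40% in positives, and a 10-point fall in experimental-arm negatives. With 70% negative, the control rate is 0.7 × 30 + 0.3 × 40 = 33%. Power is for a two-sided 5% test with 446 per arm.

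| Rise in positives | Experimental rate | Difference | Power |
|---|---|---|---|
| 0 | 0.7 × 20 + 0.3 × 40 = 26% | −7 points | 63% |
| 10 points | 0.7 × 20 + 0.3 × 50 = 29% | −4 points | 25% |
| 20 points | 0.7 × 20 + 0.3 × 60 = 32% | −1 point | about 5% |

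With 50% negative, a 10-point rise cancels the difference (35% in both arms) and a 20-point rise reverses it to +5 points. With 80% negative, a 20-point rise still leaves −4 points.

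**Precision of a comparison within positives.** With 89 to 178 positives per arm and a 30% rate, the standard error is √(0.42/89) = 0.069 to √(0.42/178) = 0.049. The 95% interval is then about ±13 to ±10 points, so the comparison would detect only a large change.

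**The case against.** A reader might infer from 8.6 that the experimental arm contains two opposite interventions, de-escalation in negatives and escalation in positives. The documents do not support that. Section 8.6 names no extra test, treatment, threshold or timing, and it says that the deviations do not concern in-hospital examinations. Its further evaluation can be read as the usual work-up that positives continue and negatives skip, since 7.1 says negatives have no further ACS evaluation. Section 9 presents intensification as a possible unwanted effect, which is compatible with standard care being the rule. All of this stands.

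The site investigator's oversight is also not the only safeguard. Section 12.1 requires checks that mandated procedures are followed and variances identified, 12.1.1 has the sponsor monitor adherence, and 14.2.3 provides for training in the management protocols. That stands as well, although a check on adherence is only as clear as the text it is made against.

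Nor does the possible mixing depend on the wording. Staff who know a positive result could act on it even if 8.6 matched 7.1 exactly. Any such reaction is part of integrating Copeptin into the process, so the randomised comparison still validly estimates the effect of the whole strategy. This is correct, and it makes the issue one of definition and interpretation, not bias.

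Finally, a table by biomarker status may sit in a statistical analysis plan that is not at hand, so its absence here is no defect in itself. The narrower observation is that the Protocol's own list of predefined subgroups omits the factor that determines care in the experimental arm.

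**Conclusion.** The contradiction holds: care of Copeptin-positive experimental patients is a deviation in 8.6 and standard care in the synopsis, section 5 and 7.1. A designed second intervention is not established, and the whole-strategy comparison remains valid. What is left unclear is what that strategy is for positives, and how a whole-arm result on angiography, PCI, bleeding or stay should be read if positives and negatives moved in opposite directions.

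A reader might also infer that intensified care of positives would make early discharge look safer than it is. The documents do not settle that. More intensive care could prevent events, or it could add PCI and CABG that count as MACE.

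The size is unknown. The range from 0.65 to 2.6 standard errors rests wholly on assumed shares, rates and shifts, and it runs from negligible to important. The severity is minor to moderate.

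**What to change.** Reconcile 8.6, and the related wording in section 9, with the synopsis, section 5 and 7.1, so that one statement governs Copeptin-positive patients in the experimental arm. Which clinical rule that should be is for the sponsor and investigators; none is proposed here.

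Add baseline Copeptin status to the predefined subgroups in 5.2.5. Compare the arms on angiography, PCI, bleeding, length of stay and 30-day MACE separately in Copeptin-positive and Copeptin-negative patients, and read the whole-arm secondary results alongside. Control-arm status comes from the laboratory values described in 8.4, released after recruitment ends. Copeptin is measured in the screening blood sample (8.3, 8.6), so status is a baseline characteristic and the arms remain comparable within each stratum. The comparison in positives shows whether knowing the result changed their care. The comparison in negatives bears directly on the safety of early discharge.

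The cost is one wording correction and one further table from data already collected. The downside is another supportive comparison of limited precision, which should be labelled as such.

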8.7 Follow-up

All patients will have a 30-day and a 90-day follow-up. Both follow-ups are telephone visits to assess:

- Survival
- MACE and bleeding complications

In case of death or hospitalization during the study period medical records will be requested. The patient will consent to this in the informed consent form.

8.8 Individual trial duration

Patients will be considered study-patients until the 90 day telephone visit has been completed.

8.9 Additional 3 hour blood test

Patients can, on an optional basis, agree to an additional, study-related blood draw at 3 hours after their initial admission. This blood sample will be used to further evaluate the kinetics of Copeptin. Additionally, Troponin will be measured to compare the two markers in these samples.

Patients who agree to the blood draw have to give their separate written consent in a special box of the informed consent form (s. attachment).

9 Risk-benefit-assessment

Copeptin negative patients might experience major adverse cardiac events after discharge, which could have been prevented in case of hospital admission, due to unrecognized acute coronary syndrome.

Precaution:

Patients for this trial are very carefully selected. Patients with concomitant diseases or conditions which require a hospitalisation as well as patients with instable angina despite maximal therapy are excluded from participation. Thus, only stable, symptom-free patients will be discharged. We cannot exclude that of these patients, some will be at risk for ACS-related complications. As a precaution, patients will only be discharged after an appointment with one of our co-operating resident cardiologists has been made via the praxis-connect system as explained in section 7.1. Thus, the onward specialist care of these patients is guaranteed. The co-operating cardiologists will be well informed and trained in all trial-matters. All patients will be re-admitted to the Emergency Department upon any suspicion of risk for complications.

Copeptin positive patients might be regarded as high-risk patients and receive more intensive treatment.

Precaution:

Management of all patients will be closely monitored by the principal investigator of each site to assure suitable care and therapy.

Potential advantages for patients in the experimental arm:

Copeptin negative patients bypass further ACS evaluation and are prevented from hospitalization. Patients might be spared an unnecessary hospital admission and antithrombotic and anticoagulant treatment with their related hazards and side-effects. Patients will profit from the personal care by the resident co-operating cardiologist.

All patients will profit from the close and intense monitoring and follow-up by an experienced clinical research team.

Potential advantages for the general public:

If the new processes are shown to be efficient, safe, cost effective and/or to improve patient contentedness this trial is a great benefit to the general public.

Additional 3 hour blood draw:

The 3 hour additional blood draw is a study related blood draw. If a venous catheter is in place, it can be used to draw the blood for this sample. Otherwise a new venous puncture is necessary which holds the small risk of pain at the puncture site, local nerve irritation, hematoma and very rarely vasovagal collapse. The risk will be minimized by putting well trained staff in charge of the blood draws.

10 Termination and subsequent treatment

10.1 Premature termination of the individual participant

- Patients who are eligible for discharge from their cardiac situation but cannot be discharged for other medical reasons will be excluded from the trial
- Patients who withdraw their consent will be excluded from the trial
- Patients who violate the protocol will be excluded from the trial

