10.3 Follow-up and continuing treatment after regular / premature termination

All patients who have not been excluded from participation will be contacted via telephone for a 30 day follow-up to assess MACE and bleeding events.

All patients will be contacted via telephone after 90 days to assess MACE and bleeding events. All efforts should be made to contact all patients for the 90 day follow-up telephone visit, if the consent to do so is granted.

11 Assessment of MACE and bleeding events

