14.1 Sample size estimation

See appendix 2

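### Randomised patients can be excluded after allocation and left out of the 30-day call, and no unconditional intention-to-treat analysis returns them to the primary comparison

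*Protocol*

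**What the plan says.** All references are to the protocol.

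- **Timing.** The synopsis describes "1:1 Randomization in two study arms with differing process management". Section 8.4 opens the sealed envelope once consent is signed. The copeptin value is requested from the laboratory only after that, and is released only for the experimental arm.
- **Exclusions after allocation.** Section 10.1, repeated in the synopsis, lists three. One is withdrawal of consent. The others are "Patients who are eligible for discharge from their cardiac situation but cannot be discharged for other medical reasons will be excluded from the trial" and "Patients who violate the protocol will be excluded from the trial". Violation is not defined. Section 6.2 already bars patients who need hospital care for other reasons, so 10.1 acts on what is found or decided after randomisation.
- **Where the criteria are invoked.** Section 7.1 says, for copeptin-negative patients in the experimental arm, "Patients who show any signs and symptoms of an acute illness requiring in-hospital treatment will not be discharged". It points to the withdrawal criteria and leaves the decision to the attending physician. The control-arm text in section 7.5 has no such step.
- **Follow-up.** Section 10.3: "All patients who have not been excluded from participation will be contacted via telephone for a 30 day follow-up". Its second paragraph calls all patients at 90 days, subject to consent. Section 8.7: "All patients will have a 30-day and a 90-day follow-up".
- **Analysis.** Section 14.2.1 provides intention-to-treat analyses only as an addition, and only when more than 10% of patients are lost during follow-up.

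**The concern.** The primary endpoint (section 5.1) is MACE within 30 days, copeptin against control, and the hypothesis (section 5) is that the copeptin process does not raise it. Section 14.2.3 relies on randomisation to deal with known and unknown confounders. A rule that removes patients for something that happens after allocation gives up that protection. Logistic adjustment does not bring back patients who are no longer in the data.

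Two endpoints are exposed. MACE includes all-cause death, so a non-cardiac illness that keeps a patient in hospital can still bear on it. Length of stay (section 5.2.4) is affected more directly, because the patients removed are ones who could not go home. If removals are more frequent in the experimental arm, both could look better there than they are. In a trial meant to show that early discharge is safe, that is the unsafe direction of error.

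**Working it through.** **1. The sections side by side**

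- Sections 8.4 and 10.1: allocation comes first and the discharge decision later, so the non-discharge and violation exclusions are post-randomisation.
- Sections 10.3 and 8.7: one restricts the 30-day contact to patients not excluded and the other covers everyone. Both cannot be followed.
- Sections 7.1 and 7.5: the withdrawal criteria are invoked in one arm only. Section 10.1 itself is worded for both arms, and a control patient cleared after standard work-up could meet it. More exclusions in the copeptin arm is therefore an inference.
- The pointer in 7.1 is to section 5.3, which is the Endpoints Committee. The withdrawal criteria are in 10.1.
- Section 14.2.1: 10% of 892 is about 89 patients. Excluding 10% of one arm is 0.10 × 446 = 44.6 patients, or 5% of the trial. Even the upper case below would not reach the trigger alone, and the section does not say whether excluded patients count as lost.

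**2. The plan's own figure**

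The synopsis gives 446 per group. Its derivation is in an appendix that is not shown, so it cannot be reproduced here. This point does not dispute it.

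**3. Illustration of size**

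The documents give no exclusion rate and no risk for excluded patients, so both are assumed. Let p be the true experimental-arm rate, e the share of that arm excluded, and r the MACE rate among those excluded, with no exclusions in control. Then

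analysed rate = (p − e·r)/(1 − e).

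Take p = 7%, which lies between the 6.4% and 7.8% cited in section 14.2.2:

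| e | r | Calculation (%) | Analysed rate | Shift (points) |
|---|---|---|---|---|
| 5% | 15% | (7.0 − 0.75)/0.95 | 6.6% | −0.4 |
| 5% | 20% | (7.0 − 1.0)/0.95 | 6.3% | −0.7 |
| 10% | 15% | (7.0 − 1.5)/0.90 | 6.1% | −0.9 |
| 10% | 20% | (7.0 − 2.0)/0.90 | 5.6% | −1.4 |
| 10% | 7% | (7.0 − 0.7)/0.90 | 7.0% | 0 |

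The same formula at the protocol's two cited rates, with excluded patients at two to three times the arm's mean risk:

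- 6.4%: shift of −0.34 to −0.67 points (5% excluded) or −0.71 to −1.42 (10% excluded).
- 7.8%: shift of −0.41 to −0.82 points (5% excluded) or −0.87 to −1.73 (10% excluded).

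If e, r and p were the same in both arms, the difference between arms would not shift.

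**4. Against the trial's precision**

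The 95% half-width for the difference at 7% is 1.96 × √(2 × 0.07 × 0.93/446) ≈ 3.3 points, so every shift at p = 7% is less than half of it.

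The error rate is more sensitive. Assume a 5-point non-inferiority margin and one-sided 0.025 (neither is in the text at hand), a control rate of 7.8% and a true experimental rate of 12.8%. Excluding 5% of the experimental arm at two to three times its mean risk (25.6% to 38.4%) raises the chance of a false non-inferiority claim from 0.025 to about 0.05-0.10. Excluding 10% raises it to about 0.10-0.31. The upper ends rest on very high assumed risks.

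**The case against.** The strongest reply has four parts.

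- **Cardiac risk.** A reader might infer that the sickest copeptin-negative patients leave the MACE count. The documents do not show that. The first exclusion in 10.1 covers patients already judged fit for discharge on cardiac grounds, and most MACE components are cardiac. Section 7.1 speaks of any acute illness, which is a wider group, and no item in 10.1 plainly excludes a patient kept in for cardiac symptoms. This stands, although all-cause death keeps MACE exposed.
- **Recoverability.** A reader might infer that follow-up ends and nothing can be repaired. That goes too far. Section 10.3 calls all patients at 90 days if consent allows, and section 8.7 requests records after any death or hospitalisation, so some 30-day events could be recovered. But nothing in the plan returns those patients to the primary comparison.
- **Protocol violation.** It is tempting to count a copeptin-negative patient kept in hospital as a violator. Section 7.1 itself provides for non-discharge in acute illness, so that is not plainly a violation. The supportable point is that the term is undefined. Nothing shows that violations cluster in one arm.
- **Size.** The shares and risks are assumptions, the calculation sets control exclusions to zero, and section 6.2 removes some of these patients beforehand. All of this stands.

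None of it defends excluding randomised patients for reasons other than withdrawn consent, or the conflict between 10.3 and 8.7. Nor is this detail left to an SAP: the protocol states who is excluded and who is called, and an SAP cannot analyse 30-day data that sites were told not to collect.

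**Conclusion.** The point holds and should be fixed. Confidence is high on three matters that rest on the text alone: exclusion after randomisation, the contradiction over the 30-day call, and the conditional status of intention-to-treat analysis.

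That the exclusions favour the copeptin arm is plausible, not established. It rests on 7.1 invoking the criteria only for copeptin-negative experimental patients, at the discretion of a physician who knows the arm and the result. The size is unknown. Under the assumed 5-10% excluded from that arm alone at a 15-20% MACE rate, a true 7% would be analysed as 5.6-6.6%, an apparent gain of 0.4 to 1.4 points. With average risk among those excluded, or identical exclusion in both arms, MACE would show no spurious difference. The effect on length of stay cannot be sized from the documents.

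**What to change.** - **Section 10.1 and synopsis:** state that these rules end only the study process. Every randomised patient stays in the trial and is followed at 30 and 90 days unless consent to follow-up is withdrawn. Define protocol violation.
- **Section 10.3:** delete the qualifier that restricts the 30-day call to patients not excluded, so that it agrees with 8.7.
- **Section 14.2.1:** make analysis of all randomised patients by assigned arm unconditional and primary, with a per-protocol set alongside it. Drop the 10% trigger.
- **Reporting:** give non-discharge and protocol deviations by arm, with reasons.
- **Section 7.1:** correct the reference to 5.3.

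The cost is amendment wording and a few more telephone calls per site. Clinical discharge decisions are unchanged, and the change does not by itself alter the stated 446 per group.
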